Step 3. Review with YAB. Drs. [name] and [name] will facilitate the review of the mLab App user interface, content, and function with the YAB. Through our review, we will ensure that the mLab App is culturally appropriate for both YMSM and YTGW. [name] will insert changes directly into the mLab App mock-ups viewed on a screen, supplemented by note-taking by study staff and audio-recorded. This allows us to confirm meaning, make revisions as necessary, and reach consensus with the YAB. [name] will probe for further discussion on feasible ways forward and to ensure that the mLab App meets the current prevention guidelines. We will incorporate the recommended changes. As a final step, we will have members of the YAB test the final mLab App after the meeting in their own settings (e.g., Home) and return any comments or additional edits within 2 weeks. Final recommendations for the user interface will be shared with [name], who will work with his team and the graphic design team at Little Green Software (see letter of support) to make the final updates to the app.

Aim 2: Evaluate the efficacy of the mLab App in improving both HIV testing rates and linkage to care versus standard preventive care in 525 Black, Latino and other young men and transgender women (inclusive of YMSM and YTGW age 18-29 years) in a 12-month multi-site trial, with randomization at each site to three groups arm 1: intervention (mLab App) (N=210); arm 2: standard of care HIV information control arm (N=210); arm 3: OraQuick home test kits only (N=105).

Hypothesis 1. Youth randomized to the mLab App arm, as compared to youth in the standard of care HIV information control arm, will have: a) increased rates of HIV testing within the first 6 months of the trial; and b) increased rates of re-testing in months 7-12 of the trial.

Hypothesis 2. The total number of youth who test HIV positive and link to care in the mLab App arm will be greater as compared to the standard of care HIV information control arm.

Hypothesis 3. The image processing in the mLab App will: 1) have no statistically significant difference in sensitivity or specificity when compared to confirmatory testing, 2) have greater sensitivity and specificity when compared to the user-submitted self-analyses.

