Sample. Our sample will include 525 Black, Latino, and other young men and transgender women (inclusive of YMSM and YTGW aged 18-29 years), with Chicago: N=180 and New York: N =345; representing the population size of each city.¹²⁸ **Statistical power and sample size calculation.** This study will use a 2:2:1 RCT design. We plan to recruit total 525 subjects (210, 210, and 105 will be in arm 1, 2, and 3, respectively). The power and sample size calculations are based on the comparison of HIV testing rates in the mLab App arm compared to the standard of care HIV information control arm for Hypothesis 1 (i.e., compare HIV testing at 6 months and re-testing during 7 to 12 months). We calculated the statistical power to detect a difference across all participants (YMSM and YTGW). Our study is not powered to detect differences in outcomes in YMSM and YTGW separately but we will analyze differences in effect by gender identity (see Data Analysis Section below). The effect size is calculated based on the findings from the FORTH RCT⁷⁵ in which self-testing resulted in a two times increase in frequency of HIV testing in high-risk MSM, and a nearly four times increase in non-recent testers compared with standard care, without reducing the frequency of facility-based HIV testing. Using a Poisson distribution, we estimated a 40% HIV testing rate over 6 months for the control group and approximately 60% HIV testing rate for the intervention group. We are using a more conservative effect size than the one **reported** previously by assuming 60% testing rate for the intervention as compared to 85% in the FORTH RCT study.⁷⁵ This 20% difference is equivalent to a medium effect size. All power calculations are based on alpha=0.05 and two-sided tests of the primary comparison and an attrition rate of 20% at 6 and 12 months. We will have at least 80% power for Hypothesis 1, to conduct two tests simultaneously (i.e., to compare HIV testing rate during the first 6 months and to compare re-testing rate during 7 to 12 months).

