self-testing) is the proportion of participants who self-report being tested for HIV in the past 6 months. The secondary goal is to collect and analyze data on the app's test interpretation performance. For the intervention arm (arm 1), we will also have data to confirm their self-report since we will have a photo image of their OraQuick test. We will assess and describe any bias in self-report of HIV testing in the intervention condition.

Follow-Up Surveys. All participants will receive a follow-up survey at 6 and 12 months after the baseline visit. The follow-up survey will be administered either in person on an iPad or, if they are unable to complete an in-person visit, remotely through a Qualtrics survey distributed via email. In total there will be three survey time points for all study participants (baseline, 6 and 12 months). Study participants will receive \$40 at baseline, \$55 at 6-month follow up, and \$75 at 12-month follow up for the time to complete the surveys.

Data Analysis. Groups 1, 2, and 3 will be described with respect to baseline characteristics (e.g., means, standard deviations, ranges, and proportions). Before beginning formal analyses, we will examine the patterns of missing data, paying special attention to the balance of missing data in the study arms. From our prior trials, we anticipate all participants will provide baseline data, 90% will provide immediate post-intervention data, and approximately 80% will complete the 6 and 12 month post-enrollment assessment. Analysis of Intervention Effects.

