All multivariate analyses will be preceded by standard descriptive bivariate analyses to describe the key variables and relationships among them. These analyses will include means, frequency tables, histograms, and examination of distributions. Frequencies and rates of HIV tests, as well as corresponding confidence intervals, will be calculated for each arm. All statistical tests will be two-sided tests with the level of significance at 0.05. Hypotheses testing will be based on logistics models to compare (1) HIV testing during the first 6 months; and (2) HIV re-testing at 7-12 months between the mLab App arm and the control (*Hypothesis 1*). We will conduct stratified analyses to examine the differences in testing uptake in subgroups (i.e., racial/ethnic, age, YMSM vs. YTGW, and risk level). Effect sizes will also be compared between arms 1 and 3 to describe differences in testing and linkage behavior attributable to the mLab app with home test distribution versus home test distribution only. Linkage to care will be measured by the percent of study participants who tested positive and

attended a first HIV care appointment at NYP/Columbia or Lurie or who provide documentation of care at another clinic and the time to link to care after positive result. Follow-up surveys for HIV positive participants will also include questions regarding positive diagnosis, such as disclosure and seeking care. For participants who test HIV positive, we will compare the rates of linkage to care between the mLab App arm and the control arm using Fisher's exact test (*Hypothesis 2*). However, because the number of positive (HIV) tests is expected to be approximately 25-40, this part of the study will not have power to detect a significant statistical difference between groups.

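### Hypothesis 1 is tested twice at two-sided 0.05 with no order, adjustment or success rule; if either part alone may be claimed, the two-sided family-wise error is up to 9.75%

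*Combined protocol and SAP*

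**What the plan says.** Under Aim 2, Hypothesis 1 predicts that youth given the app, set against those in arm 2, "will have: a) increased rates of HIV testing within the first 6 months of the trial; and b) increased rates of re-testing in months 7-12". The primary outcome "is the proportion of participants who self-report being tested for HIV in the past 6 months". It is surveyed at 6 and at 12 months, and neither survey is named as the primary time point.

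The Data Analysis section states: "Hypotheses testing will be based on logistics models to compare (1) HIV testing during the first 6 months; and (2) HIV re-testing at 7-12 months". It sets the level once for everything: "All statistical tests will be two-sided tests with the level of significance at 0.05".

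The sample size section uses the same unsplit level: "All power calculations are based on alpha=0.05 and two-sided tests of the primary comparison". It then states: "We will have at least 80% power for Hypothesis 1, to conduct two tests simultaneously". That sentence recognises that there are two tests, but it is a statement about power and sets no rule for error control.

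The available text contains no alpha split, hierarchy, gatekeeping or co-primary statement. A small part of the data safety material was not available to check; it lies outside the analysis section.

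**The concern.** The plan does not say what result would support Hypothesis 1. A report could count a significant difference in months 0-6 alone, in months 7-12 alone, or in both, and nothing written in advance rules any of these out. If either part alone is enough, the trial has two chances at a false positive on its main hypothesis, each at the full 0.05. If both are needed, there is no inflation, but then the trial cannot claim Hypothesis 1 on one period only. A reader of the final report could not tell which rule was intended. The choice affects the trial's principal efficacy claim.

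**Working it through.** **Inputs from the documents** (Aim 2, sample size and Data Analysis sections)
- Two tests of arm 1 against arm 2, each at two-sided 0.05.
- 210 per arm with 20% attrition at 6 and 12 months: 210 × 0.8 = 168 per arm.
- Testing rates over 6 months: 40% control, 60% intervention.

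**Assumptions not in the documents**
- Correlation between the two test statistics. The same participants answer at both surveys, so some correlation is likely; 0 to 0.9 is shown.
- Rates in months 7-12. None are given separately, so 40% and 60% are used again.
- No allowance for any interim look at efficacy.

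**1. The plan's own power figure.** Two-proportion test, pooled variance under the null:

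power = Φ{[0.20 − 1.96 × √(2 × 0.5 × 0.5/168)] / √[(0.4 × 0.6 + 0.6 × 0.4)/168]}
= Φ{[0.20 − 1.96 × 0.05455] / 0.05345} = Φ(1.741) = 95.9%.

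Both tests significant: 0.959² = 92.0% if independent, 92.8% at correlation 0.5. The stated floor of 80% is met on this calculation.

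**2. Error if either part alone counts.** With no effect in either period and independent tests, the chance of at least one significant result is 1 − 0.95² = 9.75%. In the app's favour only, it is 1 − 0.975² = 4.94%, against 2.5% for one test. For correlated tests, from the bivariate normal distribution:

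| Correlation (assumed) | At least one significant, either direction | At least one, in the app's favour | Both significant |
|---|---|---|---|
| 0 | 9.75% | 4.9% | 0.25% |
| 0.3 | 9.5% | 4.8% | 0.5% |
| 0.5 | 9.1% | 4.5% | 0.9% |
| 0.7 | 8.3% | 4.2% | 1.7% |
| 0.9 | 7.0% | 3.5% | 3.0% |

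Simulated binary data at 168 per arm with a 40% rate gave 10.0%, 9.8% and 9.2% at within-person correlations of 0, 0.3 and 0.5. This agrees with the second column; the small excess arises because each single test ran at about 5.1%.

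**3. Error if both parts are required.** With no effect in either period, the last column applies. With a real effect in one period only, the false claim needs the other test to be wrong, so the error cannot exceed 5%.

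**4. Power under each rule** (168 per arm)
- Fixed order, each at 0.05: 95.9% for months 0-6, about 92% for both.
- Both required, each at 0.05: about 92%.
- 0.025 per test (Bonferroni): Φ{[0.20 − 2.241 × 0.05455] / 0.05345} = Φ(1.454) = 92.7% per test. Holm is at least as powerful.

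**5. Poisson variant.** The sample size section mentions a Poisson distribution. Taking 0.40 and 0.60 as Poisson rates:

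log(0.6/0.4) / √[1/(168 × 0.4) + 1/(168 × 0.6)] = 0.405/0.157 = 2.575, and Φ(2.575 − 1.96) = 73.1% at 0.05.

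At 0.025 the same formula gives 63.1%. The outcome is a proportion and the planned model is logistic, so step 1 is the closer match to the plan.

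**The case against.** The strongest reply is that Hypothesis 1 is one hypothesis whose parts are joined by *and*, and that the power statement covers the two tests together. Read that way, both parts must succeed, the error is at most 5%, and no correction is needed. This is a fair reading and the documents do not exclude it. They do not adopt it either. The same conjunction in the Data Analysis section simply lists two analyses, and nowhere is Hypothesis 1 said to fail if only one part is significant.

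A second reply is that the plan sets 0.05 per test and never promises 5% across the pair, so each part, reported under its own label, keeps its nominal error. That is correct, and it is why the figures above are conditional. It does not settle what may be claimed for Hypothesis 1 as a whole.

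Three further points stand. The hypothesis is directional, while 9.75% counts errors in both directions. The correlation is unknown, and higher values bring the figure down. The power for both tests rests on rates that the plan gives for only one six-month period.

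A reader might infer that the trial's false-positive rate on its primary hypothesis simply is 9-10%, or that the plan breaks its own 5% limit. The documents do not support that. It would require a rule that one part is enough, and no such rule is written.

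**Conclusion.** The gap is real: two tests of Hypothesis 1, each at full two-sided 0.05, with no order, adjustment or success criterion in the available text. Its size depends on the missing rule. If either part suffices, the two-sided family-wise error lies between 7.0% (correlation 0.9) and 9.75% (independent), and the chance of a false claim favouring the app is 3.5-4.9% instead of 2.5%. If both parts are required, there is no inflation above 5%. Under either intention the remedy is the same: write the rule down. It should be settled before outcomes are compared by arm, because it governs the main claim and costs little.

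**What to change.** Add to the Aim 2 Data Analysis section: the comparison of testing in months 0-6 is the first primary test, at two-sided 0.05; re-testing in months 7-12 is tested at two-sided 0.05 only if the first is significant. Repeat the rule beside the power statement, and state there the rates assumed for months 7-12.

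Two alternatives also hold the error at 5%: Holm's procedure across the two tests, or an explicit statement that both parts must be significant. The latter is closest to the wording of the hypothesis.

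The change is one or two sentences. On the two-proportion calculation the sample size can stay as planned. If power is lower, as on the Poisson reading, the fixed order still leaves the first test at its full 0.05 and takes nothing from its power, whereas splitting alpha would. The price of the fixed order is that H1b cannot be claimed if H1a fails, even if the later difference is large; it could then be reported only descriptively.

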Scientific Premise. YMSM and YTGW currently face barriers to HIV testing in clinics (e.g., socioeconomic

Overview of Study Aims, Design and Methods. Table 1 presents an overview of the design, participants, and data analysis plan for each aim.

Scientific Rigor. We will use a careful iterative process to refine the usability and test the efficacy of the mLab App for increasing the uptake of rapid home HIV self-testing. To increase scientific rigor we will: 1) have an image of the participants’ OraQuick test result ensuring the validity of self-reported testing collected via

surveys; 2) use validated measures; 3) use a randomized design to reduce bias in study arm assignment; 4) exercise extensive retention efforts to achieve high retention and reduce selection bias; 5) publish our design and analysis plan on clinicaltrials.gov before we commence data collection; 6) publish anonymized public use data sets after primary analyses are reported. Consideration of sex as a biological variable. We do not aim to

Table 1. Overview of Design, Methods, Participants, and Data Analysis

Aim	Design/Methods	Participants	Data Analysis
1	Usability Evaluation	Heuristic evaluation: human-computer interaction experts (N=5); End-User testing: YMSM and YTGW (N=20); Youth Advisory Board (N=10)	Quantitative and qualitative summary of heuristic violations; thematic analysis of think-aloud protocol, quantitative summary of mouse clicks, time, etc.
2	Randomized controlled design	High-risk YMSM and YTGW (N=525; arm 1 n=210, arm 2 n=210, arm 3 n=105)	Descriptive statistics; Linear regression model
3	Analysis of Para Data	Data Collected through Participant use of the mLab App (N=210)	

evaluate sex differences; the justification for only including assignment of male sex at birth is that the epidemiologic data demonstrate a clear, disproportionate impact of HIV on young racial and ethnic minority men.

Aim 1: Refine the mLab App – a mobile and connected health intervention for increasing the uptake of rapid home HIV self-testing and linkage to care – by employing rapid cycle iterative design methods with feedback from human computer interaction experts (N=5), end-users (N=20), and youth advisory board members (N=10). There are three steps with refinements to the mLab App following each step. Step 1.

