Step 2. End-User Usability Evaluation. **Study Population.** Our study participants will be young men and transgender women (inclusive of YMSM and YTGW age 18-29 years) who have engaged in recent high-risk sexual behavior with a man. Inclusion criteria. (1) 18-29 years of age (see justification below); (2) assigned male sex at birth of any current gender identification; (3) understand and read English; (4) sexually active and at risk for HIV infection per CDC guidance (e.g., YMSM or YTGW and recent anal sex with men)¹⁰⁷(5) smartphone ownership; and (6) self-report being HIV-negative or unknown status.. Exclusion Criteria. (1) persons who have a known diagnosis of HIV; and (2) persons for whom the investigators determine that participation may be detrimental to the participant or to the study (e.g., severe cognitive deficit).

Justification for Key Inclusion/Exclusion Criteria. The proposed inclusion ages of 18-29 captures the upper range of the greatest increase in new infections,⁵⁴ and the youngest age is the average age when sexual initiation begins^{108, 109} (see Inclusion of Children section). We also carefully considered inclusion of participants who are taking PrEP and will exclude participants who report taking it at baseline. While there is a growing body of literature on poor PrEP adherence,¹¹⁰⁻¹¹² particularly among Blacks and Latinos (NIMHD funding priority) as these are the two racial and ethnic minority groups who are most heavily burdened by HIV,^{4, 6-8, 113} including those on PrEP at baseline would attenuate the intervention effect due to PrEP treatment guidelines, which

include HIV testing at 3-month intervals. We will be collecting data on PrEP use and self-reported adherence to PrEP as part of the trial. Individuals on PrEP at follow-up visits will be encouraged to follow their current treatment protocol with their PrEP provider, including HIV/STI testing requirements and medical visits. We will control for PrEP use at follow-up in all analyses.

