Study Enrollment. Study participants will come in to our study site in NYC or Chicago to provide informed consent, enroll, and complete a self-administered baseline survey on an iPad. Prior to enrollment into the RCT participants will be consented to screen and administered a rapid HIV test to determine eligibility. If a participant is found to be preliminary positive in the screening procedures they will be linked to care at NYP in New York or Lurie Children's Hospital in Chicago or a healthcare provider of their choice. If they are non-reactive they will be randomized and enrolled into the trial. The baseline survey will include questions on demographic characteristics; health literacy¹³¹; sexual risk behaviors including number of men (and women) they engaged in anal or oral sex with, condomless anal intercourse, as well as their HIV testing history and opinions regarding HIV testing. The baseline survey will also include questions on PEP/PrEP use and adherence, drug and alcohol use,¹³² and the HIV Risk Index.¹³³ After completing the baseline survey, study participants in all three study arms will receive condoms, an information sheet on HIV prevention, PrEP assessment, referral information for clinics that provide PrEP, and a card with the study team's contact information and the NYP/Columbia Comprehensive Care Clinic Phone/Text Number (NYC) and Northwestern/Lurie Children's Hospital (Chicago).

Randomization. After providing informed consent, youth will be randomized to study arms in a 2:2:1 ratio of : arm 1-mLab App (2), arm 2-Standard of Care HIV information arm (2), arm 3-HIV home tests (1). We will use

stratified randomization¹³⁴ to ensure equal representation between treatment groups at each study site (Chicago vs. NYC).¹³⁵ To reduce opportunities for selection bias, we will use a variable permuted randomization block design¹³⁶ where the block size itself is randomly selected (i.e., blocks of five to ten). The advantage of the permuted block design is that treatment assignment is pre-determined before the trial begins and then assignment remains static throughout the course of the trial.¹³⁷ Within each city stratum, a computer program will randomly assign each participant to the next treatment allocation from a random-permuted block randomized sequence. All **three arms** will receive standard-of-care HIV/STI testing-related risk reduction counseling, a box of condoms, PrEP assessment, and referral information for clinics that provide PrEP.

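### The Hypothesis 1 logistic models name neither the randomisation stratum nor baseline testing history, while the plan commits every analysis to adjust for PrEP use at follow-up, a post-randomisation variable

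*Combined protocol and SAP*

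**What the plan says.** - **Primary model.** Aim 2, Data Analysis: "Hypotheses testing will be based on logistics models to compare (1) HIV testing during the first 6 months", and likewise retesting in months 7 to 12, between the mLab App arm and control. No covariate is listed. Race/ethnicity, age, YMSM vs YTGW and risk level appear there only as subgroup analyses.
- **Stratum.** Aim 2, Randomization, stratifies by Chicago vs NYC "to ensure equal representation between treatment groups at each study site".
- **Baseline data.** Aim 2, Study Enrollment: the baseline survey covers sexual risk behaviour "as well as their HIV testing history and opinions regarding HIV testing".
- **The one committed covariate.** The justification of the key inclusion and exclusion criteria (Aim 1, Step 2) says "We will control for PrEP use at follow-up in all analyses".
- **Eligibility.** The additional Aim 2 criteria exclude anyone with an HIV test in the six months before entry and anyone currently taking PrEP.
- **Table 1, Aim 2 row.** The analysis is given as "Descriptive statistics; Linear regression model", although the primary outcome is a self-reported yes/no.

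**The concern.** Two analysts could fit different primary models and both claim to follow this plan: arm only, arm plus follow-up PrEP use, or the linear model in Table 1. A primary analysis should leave no such choice open once data are in hand.

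The covariate the plan does commit to is the wrong kind. PrEP use at follow-up arises after randomisation. The app carries PrEP content, and the plan itself notes that PrEP guidelines require HIV tests every three months. Follow-up PrEP use may therefore respond to arm and also drive the outcome. Conditioning on it can remove part of the intervention effect or introduce bias, and the result no longer estimates the effect of assignment that the plan's intention-to-treat principle calls for.

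Meanwhile two variables fixed before randomisation are left unnamed. One defines the randomisation. The other, earlier testing, may predict later testing, so the comparison may lose some precision.

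**Working it through.** **Step 1. Reproduce the stated power.** Inputs from Aim 2, Statistical power: 210 per arm in the primary comparison; "alpha=0.05 and two-sided tests of the primary comparison and an attrition rate of 20% at 6 and 12 months"; and "we estimated a 40% HIV testing rate over 6 months for the control group and approximately 60% HIV testing rate for the intervention group". The stated power is at least 80%.

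Evaluable per arm: 210 × 0.8 = 168.

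Power = Φ{(|p₁ − p₂| − z·√[2p̄(1 − p̄)/n]) / √[(p₁(1 − p₁) + p₂(1 − p₂))/n]}

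- 40% vs 60%, α = 0.05: (0.200 − 1.96 × 0.05455)/0.05345 = 1.741, so power is 95.9%.
- α = 0.025: (0.200 − 2.241 × 0.05455)/0.05345 = 1.454, so power is 92.7%.
- Both tests, if independent: 0.959² = 92.0%, or 0.927² = 85.9% at α = 0.025.
- 40% vs 55%, α = 0.05: (0.150 − 1.96 × 0.05449)/0.05387 = 0.802, so power is 78.9%.

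The plan's figure holds as a lower bound.

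**Step 2. Site alone.** Site sizes are 180 and 345, so f = 180/525 = 0.343 and f(1 − f) = 0.2253. If testing rates differed by 15 points between sites (assumed), site would explain 0.2253 × 0.15²/0.25 = 2.0% of outcome variance. Omitting it would overstate the standard error by 1/√(1 − 0.0203) − 1 = 1.0%. In simulation (3,000 trials per setting, 168 per arm, balanced by site), adding site changed power by less than 0.1 point even at a site odds ratio of 2, with relative efficiency 1.00.

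**Step 3. Site plus testing history.** The documents give no prognostic strength, so a range is assumed: history prevalence 50%, history odds ratio (OR) 1 to 9, site OR 1 to 2. Power is shown as arm only → arm + site + history. Relative efficiency is for the standardised risk difference.

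| History OR | Relative efficiency | 40% vs 60% | 40% vs 55% |
|---|---|---|---|
| 1 (site OR 1) | 1.00 | 96.7 → 96.3% | 80.4 → 79.2% |
| 2 (site OR 1.5) | 1.02 | 95.8 → 95.8% | 80.5 → 80.6% |
| 3 (site OR 2) | 1.06–1.08 | 96.6 → 97.2% | 81.0 → 82.7% |
| 5 (site OR 1.5) | 1.14–1.16 | 96.5 → 97.9% | 80.9 → 83.9% |
| 9 (site OR 2) | 1.28–1.30 | 96.3 → 99.1% | 80.1 → 88.9% |

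Simulation error for a single power near 80% is √(0.8 × 0.2/3000) = 0.7 point. With no effect, the arm + site + history model rejected in 4.6% to 5.1% of trials.

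**Step 4. Cross-check by formula at history OR 5.** Effective n is 168 × 1.163 = 195.4 at 40% vs 60%, giving 97.9% against 95.9% (+2.0 points). It is 168 × 1.142 = 191.9 at 40% vs 55%, giving 84.0% against 78.9% (+5.1 points). The adjusted powers agree with the simulation. The gains look larger because the formula puts unadjusted power one to two points below its simulated value.

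**Step 5. Does history still vary after eligibility?** The baseline version of the primary outcome is the same for everyone, so only longer-term history can differ. Background figures for ever tested and tested in the past year are 61.8% and 21.6% (cisgender gay and bisexual men) and 35.6% and 10.0% (transgender women). Removing past-year testers leaves (61.8 − 21.6)/78.4 = 51% and (35.6 − 10.0)/90.0 = 28% ever tested. These are not trial participants, but they suggest the variable would not be constant.

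**Step 6. Follow-up PrEP use.** No size can be computed, because the documents give neither uptake by arm nor its link with testing. The reasoning is from the text: PrEP users are excluded at entry, so all PrEP use at follow-up starts after entry. All arms receive PrEP assessment and referral, and the app adds PrEP material.

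**The case against.** The case against is substantial.

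- **Silence is not a stated unadjusted model.** A reader might infer that the plan fixes an arm-only analysis. It does not: it mentions multivariate analyses and promises one covariate elsewhere. The defect is incomplete specification. This stands.
- **The power at stake is small.** A reader might infer that the trial gives up substantial free precision or is underpowered. Power for one test is about 96% at the planned effect, and the gain is essentially nil at a history OR of 2 or below. This stands.
- **Testing history cannot be called the strongest baseline predictor.** Eligibility truncates it, everyone randomised has just had a rapid test at screening, and no prognostic estimate is given. The larger effect in non-recent testers, taken from the self-testing trial cited for the effect size, is a subgroup treatment effect and says nothing direct about prognosis. This stands.
- **Omitting site does no visible harm.** The excess standard error is about 1% in Step 2. This stands, with one qualification: blocking balances those randomised, whereas the simulation assumes balance among the 80% who complete.
- **Adjustment does not shrink the standard error of a log odds ratio**, and it changes the odds ratio from marginal to conditional. This is correct, so the primary estimate must be named.
- **The PrEP sentence sits in the Aim 1 text.** That does not help, because Aim 1 has no follow-up visits. The sentence concerns the trial, and its wording covers every analysis.

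**Conclusion.** The point holds as one of pre-specification. The models for both Hypothesis 1 tests name neither the stratification factor nor a baseline covariate the trial already collects, the only committed adjustment is post-randomisation, and Table 1 names a different kind of model.

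The precision argument is secondary and conditional. Site gives no measurable gain. For assumed history odds ratios up to 5 at 50% prevalence, simulation gives about 0 to 1.5 power points at 40% vs 60% and about 0 to 3 at 40% vs 55%. The variance formula puts the upper ends at about 2 and 5. If history is unrelated to later testing there is no gain, and simulated power was up to about a point lower. These figures assume 168 evaluable per arm, balance by site, and α of 0.05 per test.

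The documents do not show that the stated power is wrong, that Type I error is inflated, or that the conclusion would turn on baseline adjustment. Bias from adjusting for follow-up PrEP use is possible, but neither its size nor its direction can be derived from the documents.

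**What to change.** 1. State the primary model for both Hypothesis 1 tests as logistic regression of tested (yes/no) on arm, site and one defined baseline testing-history variable. Define its categories in advance from ever tested and time since last test, given the six-month exclusion.
2. Make the standardised (marginal) risk difference with 95% CI the primary estimate, and report the odds ratio alongside it.
3. Replace the commitment to control for follow-up PrEP use in all analyses with a labelled sensitivity analysis, so that the plan does not contradict the new primary model.
4. Change the Aim 2 row of Table 1 from a linear to a logistic model.

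The cost is analysis-plan wording only. Site and testing history are already collected, sample size is unchanged, and simulated Type I error stays at about 5%. The change should be made before outcome data by arm are examined.
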